12. Have a Grade 3 or greater laboratory abnormality based on the protocol toxicity scale (Section 10.2.1) except for the following that are allowed:

- a) Stable Grade 3 prothrombin time (PT) secondary to warfarin treatment.
- b) Stable Grade 3 partial thromboplastin time (PTT) due to lupus anticoagulant and not related to liver disease or anti-coagulant therapy.
- c) Stable Grade 3 hypoalbuminemia due to lupus nephritis and not related to liver disease or malnutrition.
- d) Any grade proteinuria
- e) Stable Grade 3 gamma glutamyl transferase (GGT) elevation due to lupus hepatitis and not related to alcoholic liver disease, uncontrolled diabetes or viral hepatitis. If present, any abnormalities in the ALT and/or AST must be ≤Grade 2.
- f) Stable Grade 3 neutropenia; or stable Grade 3 lymphopenia; or stable Grade 3 leukopenia, due to SLE

13. Have a history of an anaphylactic reaction to parenteral administration of contrast agents, human or murine proteins or monoclonal antibodies.

14. Have evidence of serious suicide risk including any history of suicidal behaviour in the last 6 months or who in the investigator's judgment, poses a significant suicide risk.

Prior/Concomitant Therapy

15. Have received treatment with belimumab at any time.

16. Have received any of the following within 364 days of Day 0:

- a) Treatment with any B-cell targeted therapy (e.g., rituximab, other anti-CD20 agents, anti-CD22 [epratuzumab], anti-CD52 [alemtuzumab], BLyS-receptor fusion protein [BR3], TACI-Fc)
- b) Abatacept
- c) A biologic investigational agent

17. Have required 3 or more courses of systemic corticosteroids for concomitant conditions (e.g., asthma, atopic dermatitis) within 90 days of Day 0 (Topical or inhaled steroids are permitted).

18. Have received any of the following within 90 days of Day 0:

- a) Anti-Tumour Necrosis Factor (TNF) or anti-IL-6 therapy (e.g., adalimumab, etanercept, infliximab, tofacitinib, certolizumab, golimumab)
- b) Interleukin-1 receptor antagonist (anakinra)
- c) Intravenous immunoglobulin (IVIG)
- d) Plasmapheresis

19. Have received any of the following within 30 days of Day 0:

- a) Intravenous (IV) cyclophosphamide
- b) A non-biologic investigational agent (30 days window OR 5 half-lives, whichever is longer)
- c) Any new immunosuppressive/immunomodulatory agent, anti-malarial, NSAID (See Inclusion Criteria #5)
- d) High dose prednisone or equivalent (>1.5 mg/kg/day) or any intramuscular or intravenous steroid injection

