7.1.2. IgG Stopping Criteria

Any participant who has a Grade 4 IgG level, by the protocol-defined Adverse Event and Laboratory Value Severity Grade Scale (see Appendix 2, Section 10.2.1), will have dosing with study agent withheld, and the appropriateness to continue study treatment must be discussed with the Medical Monitor before the next dose. Any participant who has a Grade 4 IgG level associated with a severe or serious infection will have study agent discontinued and should complete the follow-up assessments as described in the SoA (Section 1.2).

7.1.3. **Rechallenge**

7.1.3.1. **Study Intervention Restart or Rechallenge after liver stopping criteria met**

Study intervention restart or rechallenge after liver chemistry stopping criteria are met by any participant in this study is not allowed.

7.1.4. **Temporary Discontinuation**

In the event of a participant experiencing an AE or SAE, the investigator may at their discretion choose to instruct the participant/caregiver to skip one or more scheduled administrations of belimumab. If a participant misses 3 or more consecutive belimumab infusions, participant will be withdrawn from belimumab treatment.

7.2. **Participant Discontinuation/Withdrawal from the Study**

- A participant may withdraw from the study at any time at his/her own request or may be withdrawn at any time at the discretion of the investigator for safety, behavioural, compliance or administrative reasons. This is expected to be uncommon.
- At the time of discontinuing from the study, if possible, an early discontinuation or exit visit should be conducted, as shown in the SoA (Section 1.2) for data to be collected at the time of study discontinuation and follow-up and for any further evaluations that need to be completed.
- The participant will be permanently discontinued both from the study intervention and from the study at that time.
- If the participant's parent/caregiver withdraws consent for disclosure of future information, the sponsor may retain and continue to use any data collected before such a withdrawal of consent.
- If a participant withdraws from the study, her/his parent/caregiver may request destruction of any samples taken and not tested, and the investigator must document this in the site study records.

7.3. **Lost to Follow-Up**

A participant will be considered lost to follow-up if he or she repeatedly fails to return for scheduled visits and is unable to be contacted by the study site.

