Hypokalaemia	3.0-3.4 meq/L	2.5-2.9 meq/L	2.0-2.4 meq/L	< 2.0 meq/L
Hyperkalaemia	5.6-6.0 meq/L	6.1-6.5 meq/L	6.6-7.0 meq/L	> 7.0 meq/L
Phosphate				
Hypophosphatemia	2.0-2.4 mg/dL	1.5-1.9 mg/dL	1.0-1.4 mg/dL	< 1.0 mg/dL
Calcium- (Corrected For Albumin)				
Hypocalcaemia	7.8-8.4 mg/dL	7.0-7.7 mg/dL	6.1-6.9 mg/dL	< 6.1 mg/dL
Hypercalcemia	10.6-11.5 mg/dL	11.6-12.5 mg/dL	12.6-13.5 mg/dL	>13.5 mg/dL
Magnesium				
Hypomagnesemia	1.2-1.4 meq/L	0.9-1.1 meq/L	0.6-0.8 meq/L	< 0.6 meq/L
Albumin				
Hypoalbuminemia	3.00-3.49 g/dL	2.50-2.99 g/dL	2.00-2.49 g/dL	< 2.00 g/dL
Bilirubin (Total)				
Hyperbilirubinemia (Total)	> 1.0-1.5 x ULN	> 1.5-2.5 x ULN	> 2.5-5 x ULN	> 5 x ULN
Glucose				
Hypoglycaemia	55-64 mg/dL	40-54 mg/dL	30-39 mg/dL	< 30 mg/dL
Hyperglycaemia (nonfasting & no prior diabetes)	116-160 mg/dL	161-250 mg/dL	251-500 mg/dL	> 500 mg/dL
Triglycerides	151-399 mg/dL	400-750 mg/dL	751-1200 mg/dL	> 1200 mg/dL
Creatinine	> 1.0-1.5 x ULN	> 1.5-3.0 x ULN	> 3.0-6.0 x ULN	> 6.0 x ULN

Adverse Event and Laboratory Value Severity Grade Table (continued)

	GRADE 1 MILD	GRADE 2 MODERATE	GRADE 3 SEVERE	GRADE 4 POTENTIALLY LIFE-THREATENING
CHEMISTRIES (continued)				
Uric Acid				
Hyperuricemia	7.5-10.0 mg/dL	10.1-12.0 mg/dL	12.1-15.0 mg/dL	> 15.0 mg/dL
Liver Transfases (AST, ALT, and GGT)	1.25-2.5 x ULN	> 2.5-5.0 x ULN	> 5.0-10.0 x ULN	> 10.0 x ULN
Alkaline Phosphatase	1.25-2.5 x ULN	> 2.5-5.0 x ULN	> 5.0-10.0 x ULN	> 10.0 x ULN
Pancreatic Enzymes				
Amylase	> 1.0-1.5 x ULN	> 1.5-2.0 x ULN	> 2.0-5.0 x ULN	> 5.0 x ULN
Pancreatic amylase	> 1.0-1.5 x ULN	> 1.5-2.0 x ULN	> 2.0-5.0 x ULN	> 5.0 x ULN
Lipase	> 1.0-1.5 x ULN	> 1.5-2.0 x ULN	> 2.0-5.0 x ULN	> 5.0 x ULN
Hypoglobulinemia (IgG)*	550-700 mg/dL	400-549 mg/dL	250-399 mg/dL	< 250 mg/dL

(continued)

*[Eibl, 1995; Goldfarb, 2001; Yamani, 2001].

Adverse Event and Laboratory Value Severity Grade Table (continued)

GASTROINTESTINAL	GRADE 1 MILD	GRADE 2 MODERATE	GRADE 3 SEVERE	GRADE 4 POTENTIALLY LIFE- THREATENING
Nausea	Mild OR transient; reasonable intake maintained	Mod discomfort OR intake decreased for < 3 days	Severe discomfort OR minimal intake for ≥ 3 days	Hospitalisation required

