10.5. Appendix 5: Liver Safety: Required Actions and Follow-up Assessments

Phase 3-4 liver chemistry stopping, and increased monitoring criteria have been designed to assure participant safety and evaluate liver event aetiology

Phase 3/4 liver chemistry stopping criteria and required follow up assessments

Liver Chemistry Stopping Criteria	
ALT-absolute	ALT \geq 8xULN
ALT Increase	ALT \geq 5xULN but <8 xULN persists for ≥ 2 weeks ALT \geq 3xULN but <5 xULN persists for ≥ 4 weeks
Bilirubin^{1, 2}	ALT \geq 3xULN and bilirubin \geq 2xULN ($>35\%$ direct bilirubin)
INR²	ALT \geq 3xULN and INR >1.5
Cannot Monitor	ALT \geq 5xULN but <8 xULN and cannot be monitored weekly for ≥ 2 weeks ALT \geq 3xULN but <5 xULN and cannot be monitored weekly for ≥ 4 weeks
Symptomatic³	ALT \geq 3xULN associated with symptoms (new or worsening) believed to be related to liver injury or hypersensitivity
Required Actions and Follow up Assessments	
Actions	

 • Immediately discontinue study intervention • Report the event to GSK within 24 hours • Complete the liver event CRF and complete an SAE data collection tool if the event also meets the criteria for an SAE² • Perform liver event follow up assessments • Monitor the participant until liver chemistries resolve, stabilise, or return to within Baseline (see MONITORING below) • Do not restart/rechallenge participant with study intervention. Permanently discontinue study intervention and continue participant in the study for any protocol specified follow up assessments. 	
 • Viral hepatitis serology⁴ • Obtain INR and recheck with each liver chemistry assessment until the transaminases values show downward trend • Obtain blood sample for pharmacokinetic (PK) analysis, within 6 weeks after last dose⁵ • Serum creatine phosphokinase (CPK) and lactate dehydrogenase (LDH). • Fractionate bilirubin, if total bilirubin ≥ 2xULN • Obtain complete blood count with differential to assess eosinophilia

Liver Chemistry Stopping Criteria	

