
MONITORING:
 
For bilirubin or INR criteria:
 
 Repeat liver chemistries (include ALT, AST, alkaline phosphatase, bilirubin and INR) and perform liver event follow up assessments within 24 hours Monitor participant twice weekly until liver chemistries resolve, stabilise or return to within Baseline A specialist or hepatology consultation is recommended 
For All other criteria:
 
 Repeat liver chemistries (include ALT, AST, alkaline phosphatase, bilirubin and INR) and perform liver event follow up assessments within 24-72 hours Monitor participant weekly until liver chemistries resolve, stabilise or return to within Baseline 	
 Record the appearance or worsening of clinical symptoms of liver injury, or hypersensitivity, on the AE report form Record use of concomitant medications on the concomitant medications report form including acetaminophen, herbal remedies, other over the counter medications. Record alcohol use on the liver event alcohol intake case report form (CRF) page 
For bilirubin or INR criteria:
 
 Anti-nuclear antibody, anti-smooth muscle antibody, Type 1 anti-liver kidney microsomal antibodies, and quantitative total immunoglobulin G (IgG) or gamma globulins. Liver imaging (ultrasound, magnetic resonance, or computerised tomography) and /or liver biopsy to evaluate liver disease: complete Liver Imaging and/or Liver Biopsy CRF forms.

1. Serum bilirubin fractionation should be performed if testing is available. If serum bilirubin fractionation is not immediately available, discontinue study intervention for that participant if ALT $\geq 3 \times \text{ULN}$ and bilirubin $\geq 2 \times \text{ULN}$. Additionally, if serum bilirubin fractionation testing is unavailable, **record presence of detectable urinary bilirubin on dipstick**, indicating direct bilirubin elevations and suggesting liver injury.
2. All events of ALT $\geq 3 \times \text{ULN}$ and bilirubin $\geq 2 \times \text{ULN}$ ($>35\%$ direct bilirubin) or ALT $\geq 3 \times \text{ULN}$ and INR > 1.5 which may indicate severe liver injury (possible 'Hys Law'), **must be reported as an SAE (excluding studies of hepatic impairment or cirrhosis)**; the INR threshold value stated will not apply to participants receiving anticoagulants

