3. New or worsening symptoms believed to be related to liver injury (such as fatigue, nausea, vomiting, right upper quadrant pain or tenderness, or jaundice) or believed to be related to hypersensitivity (such as fever, rash or eosinophilia)
4. Includes: Hepatitis A Immunoglobulin M (IgM) antibody; HBsAg and HBcAb (conduct quantitative Hepatitis B DNA test if positivity for HBsAg and/or HBcAb); hepatitis C RNA; cytomegalovirus IgM antibody; Epstein-Barr viral capsid antigen IgM antibody (or if unavailable, heterophile antibody or monospot testing); and hepatitis E IgM antibody.
5. Record the date/time of the PK blood sample draw and the date/time of the last dose of study intervention prior to the PK blood sample draw on the CRF. If the date or time of the last dose is unclear, provide the participant's best approximation. If the date/time of the last dose cannot be approximated OR a PK sample cannot be collected in the time period indicated above, do not obtain a PK sample. Instructions for sample handling and shipping are in the SRM.

Phase 3/4 liver chemistry increased monitoring criteria with continued therapy

Liver Chemistry Increased Monitoring Criteria – Liver Monitoring Event	
Criteria	Actions

ALT \geq5xULN and <8xULN and bilirubin <2xULN without symptoms believed to be related to liver injury or hypersensitivity, and who can be monitored weekly for 2 weeks.
 
OR
 
ALT \geq3xULN and <5xULN and bilirubin <2xULN without symptoms believed to be related to liver injury or hypersensitivity, and who can be monitored weekly for 4 weeks.
	
 Notify the GSK medical monitor within 24 hours of learning of the abnormality to discuss participant safety. Participant can continue study intervention Participant must return weekly for repeat liver chemistries (ALT, AST, alkaline phosphatase, bilirubin) until they resolve, stabilise or return to within Baseline If at any time participant meets the liver chemistry stopping criteria, proceed as described above If ALT decreases from ALT \geq5xULN and <8xULN to \geq3xULN but <5xULN, continue to monitor liver chemistries weekly. If, after 4 weeks of monitoring, ALT <3xULN and bilirubin <2xULN, monitor participants twice monthly until liver chemistries normalise or return to within Baseline.

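### Exclusion 12 admits a child with ALT ≥3xULN and bilirubin ≥2xULN who can already meet a permanent liver stopping row; isolated stable ALT of 3 to <5xULN is admitted, then stopped at 4 weeks

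*Protocol*

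**What the plan says.** **Entry.** Protocol Section 5.2, exclusion 12, removes children with a Grade 3 or higher laboratory value, with listed exceptions. Exception 12(e) allows a stable Grade 3 GGT due to lupus hepatitis and adds: "If present, any abnormalities in the ALT and/or AST must be ≤Grade 2". The general rule gives the same ALT limit outside that exception.

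**Grading.** Section 10.2.1 grades ALT in the row "Liver Transfases (AST, ALT, and GGT"), where Grade 2 is above 2.5 and up to 5.0xULN. Grade 2 total bilirubin is above 1.5 and up to 2.5xULN.

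**Stopping.** Appendix 5 (Section 10.5) requires an immediate stop for, among others:
- ALT at or above "5xULN but <8 xULN persists for" at least 2 weeks;
- ALT at or above "3xULN but <5 xULN persists for" at least 4 weeks;
- ALT ≥3xULN with bilirubin ≥2xULN and more than 35% direct, with no persistence requirement.

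Footnote 1 widens the bilirubin row: "If serum bilirubin fractionation is not immediately available, discontinue study intervention for that participant if ALT" is ≥3xULN and bilirubin ≥2xULN. Section 7.1.3.1 makes the stop final: "Study intervention restart or rechallenge after liver chemistry stopping criteria are met by any participant in this study is not allowed".

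**Continued dosing under monitoring.** Appendix 5 lets a child without symptoms stay on treatment with weekly tests at ALT 3 to <5xULN, but only with bilirubin <2xULN. Testing goes on "until they resolve, stabilise or return to within Baseline". The same box adds: "If at any time participant meets the liver chemistry stopping criteria, proceed as described above".

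**The concern.** The entry limit and the stopping limits are set on different scales, toxicity grade against multiples of ULN, and the protocol does not reconcile them. The visible stopping rows do not ask whether the value has changed since entry. Baseline appears only as a point at which monitoring may end, never as an exemption from stopping.

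A child could therefore be enrolled with no criterion breached, exposed to belimumab, and permanently withdrawn from it for a liver value no different from the one accepted at screening. The combined ALT and bilirubin pattern matters most, because Appendix 5 itself flags it (with more than 35% direct bilirubin) as possible severe liver injury. No fixed entry criterion keeps such a child from a first dose.

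**Working it through.** This is a comparison of ranges, followed by a count of infusions. The plan states no figure of its own to reproduce.

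**Step 1. Eligible ranges (Sections 5.2 and 10.2.1).** Grade 2 or lower means ALT ≤5.0xULN and total bilirubin ≤2.5xULN.

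**Step 2. Lowest ALT at which a visible stopping row can be met (Appendix 5).**

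| Row | Minimum ALT | Other condition |
|---|---|---|
| ALT-absolute | 8xULN | none |
| ALT Increase, 2-week | 5xULN | persistence |
| ALT Increase, 4-week | 3xULN | persistence |
| Bilirubin | 3xULN | bilirubin ≥2xULN, >35% direct or not fractionated |
| INR | 3xULN | INR >1.5 |
| Cannot Monitor | 3xULN or 5xULN | weekly tests not possible |
| Symptomatic | 3xULN | new or worsening symptoms |

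The minimum over all rows is 3xULN. The label ALT Increase might suggest change from Baseline, but both criteria under it are plain multiples of ULN.

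**Step 3. Overlap for the combination.**
- ALT: ≤5.0 and ≥3.0 gives 3.0 to 5.0xULN.
- Bilirubin: ≤2.5 and ≥2.0 gives 2.0 to 2.5xULN.

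A child in both ranges, with more than 35% direct bilirubin or no fractionation to hand, is eligible and meets the bilirubin row at once. The monitoring pathway is closed to that child because it requires bilirubin <2xULN.

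**Step 4. Overlap for ALT alone.** The 4-week band, 3.0 to <5.0xULN, lies wholly inside the eligible range (≤5.0xULN). With bilirubin <2xULN and no symptoms, the child may be dosed under weekly tests. An unchanged value can already satisfy the condition for ending those tests, yet the stopping rows still override. Monitoring defers the stop but does not prevent it.

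**Step 5. Infusions received (Section 6.1 schedule).**
- Planned: Days 0 and 14, then every 28 days from Day 28 to Day 336. (336 − 28)/28 + 1 = 12, and 2 + 12 = 14.
- Combination: chemistry is drawn on Day 0. If the child is dosed that day and the rule is applied when the result returns, 1 of 14.
- Stable ALT 3 to <5xULN, clock from Day 0: 4 weeks is Day 28. Infusions before Day 28 are those on Days 0 and 14, so 2 of 14. If the Day 28 infusion is given before that day's result is known, 3 of 14.

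The protocol does not say whether pre-treatment values count towards persistence. The 2-or-3 count assumes that they do not.

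**The case against.** The best defence is that the two rules do different jobs. Exclusion 12 limits a value at entry; the 4-week row limits persistence on treatment. Read together, they admit Grade 2 ALT, test weekly, and stop if it has not fallen below 3xULN by 4 weeks. That is a coherent, cautious policy for children, and an absolute threshold can be a deliberate safety choice. ALT need not stay put either: SLE therapy is fixed for 30 days before Day 0, but Section 6.5.1 lets the investigator change concurrent drugs from Day 0. For isolated ALT this argument largely stands. A reader might infer that the rules contradict each other and that every child with ALT ≥3xULN must be excluded. The documents do not support that: both rules can be followed for every child, and 12(e) expressly tolerates Grade 2 ALT.

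The defence does not reach the combination. The bilirubin row has no persistence window, so there is no period in which the value can settle.

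Existing exclusions shrink the group without closing the gap. Exclusion 4 covers hepatic disease not due to SLE, so it misses lupus hepatitis. Exclusions 26 and 27 remove hepatitis B and C. Exclusion 5 allows a laboratory abnormality to exclude at the investigator's discretion, but sets no ALT or bilirubin limit.

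Finally, Section 7.1.1 also ties discontinuation to Algorithms A and B, which are not shown. A Baseline term there cannot be ruled out. The visible Algorithm B caption uses absolute ULN multiples, as Appendix 5 does.

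**Conclusion.** The point holds, as a minor one, on the visible text. The firm part is the combination: a child with ALT ≥3xULN and bilirubin ≥2xULN, more than 35% direct or not fractionated, passes exclusion 12 while already meeting an immediate and permanent stopping row, and could be dosed once. The softer part is isolated ALT: a stable 3 to <5xULN leads to a permanent stop after 2 or 3 of 14 infusions, counting from Day 0. This may be intended, but the protocol does not say so.

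The conclusion assumes that Algorithms A and B contain no Baseline exemption. The documents give no count of children affected, and it may be zero.

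Two further inferences are not supported. A reader might suppose that the unchanged entry pattern would have to be reported as an SAE, since Appendix 5 footnote 2 says such events must be. Section 8.4.1, however, sends occurrences that begin after consent but before treatment to medical history, and the definitions in Section 10.3 leave the matter unclear, so no SAE consequence is claimed. A reader might also suppose that the primary endpoints are affected; with the number of children unknown, nothing in the documents shows that.

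**What to change.** **Combination.** Add to Section 5.2, exclusion 12: *children with screening ALT ≥3xULN together with total bilirubin ≥2xULN (more than 35% direct, or not fractionated) are excluded, even if each value is Grade 2.* This costs one sentence and one line on the screening checklist. ALT and total bilirubin are already in the screening chemistry, and the wording covers the case where no direct fraction is available.

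**Isolated ALT ≥3xULN.** The sponsor should align the two limits in one of two ways:
- *Entry limit of ALT <3xULN*, with the last sentence of 12(e) changed to match. This is the simplest route. No visible stopping row can be met below 3xULN, so it would also cover the combination. The cost is a few more screen failures, including some children with lupus hepatitis whose ALT would have settled within 4 weeks and who could have continued under the present rule. A child just under 3xULN at screening and just over it on Day 0 would still fall under the existing rows; Section 5.5 already allows borderline screening values to be repeated.
- *Baseline-multiple stopping thresholds* for children admitted at or above 3xULN. This keeps children with stable lupus hepatitis, but needs a change to Appendix 5 and, for consistency, a check of Algorithms A and B.

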5.3. Lifestyle Considerations

No lifestyle restrictions are required during the course of this study.

5.4. Screen Failures

Screen failures are defined as participants who consent to participate in the clinical study but are not subsequently entered in the study. A minimal set of screen failure information is required to ensure transparent reporting of screen failure participants to meet the Consolidated Standards of Reporting Trials (CONSORT) publishing requirements and to

respond to queries from regulatory authorities. Minimal information includes demography, screen failure details, eligibility criteria, any protocol deviations and any serious adverse events (SAEs).

Individuals who do not meet the criteria for participation in this study (screen failure) may be rescreened once at the investigator's discretion following discussion with the medical monitor. Such participants will be assigned a new participant number and all screening assessments will be repeated.

5.5. Repeat Assessments during the 35 Day Screening Period

Laboratory assessments may be repeated if determined necessary by the investigator, for example: (a) in cases of technical malfunction (e.g., loss of laboratory specimen), (b) in the event of a value close enough to the exclusionary threshold that it may reasonably lie within the degree of variability of the assay; (c) if there is reason to believe the result may be false (e.g. contradicts recent result for the same parameter).

These are repeat assessments and not rescreening events. If the original result was exclusionary and is confirmed by a repeat test, the participant will be excluded.

